4.3 Alternatives

Patients will be monitored at routine clinic follow-up visits. They are counseled on warning signs that should prompt a call to their physician, and provided with a phone number at which they can reach a physician for advice at all hours. None of these methods of protection jeopardizes patient confidentiality beyond the risks inherent in routine patient care. A study participant may undergo the alternative (i.e., forego LYMPHA) if she chooses to withdraw from the study.

5. INVESTIGATIONAL AGENT/DEVICE/PROCEDURE INFORMATION

5.1 Investigational Agent/Device/Procedure

As described in section 2.2, the intervention arm involves the use of the LYMPHA procedure at the time of axillary lymphadenectomy, specifically, anastomosing lymphatics to nearby veins distal to the site of injury to facilitate normal lymphatic drainage [11]. This procedure is a normal part of clinical management for this condition. The purpose of this study is to more accurately elucidate the efficacy and role of this procedure. Nanofibrillar collagen scaffolds are FDA approved product for soft tissue reinforcement and is routinely used for this indication at the surgical site to enhance tissue repair.

5.2 Availability

No applicable

5.3 Agent Ordering

Not applicable

5.4 Agent Accountability

Not applicable

6. DOSE MODIFICATIONS

Not applicable

A Randomized Clinical Trial of the LYMPHA procedure for the Prevention of Lymphedema after Axillary Lymphadenectomy

7. ADVERSE EVENTS AND REPORTING PROCEDURES

7.1 Potential Adverse Events

Potential risks of LYMPHA include the baseline risks of surgical intervention, including but not limited to bleeding, infection, scar, injury to surrounding structures, risks of anesthesia, and need for further surgery. The investigation, as designed, is deemed to have a low potential for risk. Only cut lymphatics will be repaired. The LYMPHA procedure is used now in several clinical centers without reported complications [12, 19, 29].

7.2 Adverse Event Reporting

Adverse events will be graded according to CTCAE v4.03. Both Serious and Non-Serious Adverse Events will be clearly noted in source documentation and listed on study specific Case Report Forms (CRFs). The Protocol Director (PD) or designee will assess each Adverse Event (AE) to determine whether it is unexpected according to the Informed Consent, Protocol Document, or Investigator's Brochure, and related to the investigation. All Serious Adverse Events (SAEs) will be tracked until resolution, or until 30 days after the last dose of the study treatment.

SAEs CTCAE Grade 3 and above, and all subsequent follow-up reports will be reported to the Stanford Cancer Institute Data and Safety Monitoring Committee (DSMC) using the study specific CRF regardless of the event's relatedness to the investigation. Following review by the DSMC, events meeting the IRB definition of 'Unanticipated Problem' will be reported to the IRB using eProtocol within 10 working days of DSMC review, or within 5 working days for deaths or life-threatening experiences.

8. CORRELATIVE/SPECIAL STUDIES

There are no planned correlative studies at this time

A Randomized Clinical Trial of the LYMPHA procedure for the Prevention of Lymphedema
after Axillary Lymphadenectomy

9. STUDY CALENDAR

	Pre-Study	Intervention	Intervention follow-up	Post-op Wk 1 ^c	Post-op Wk 24 ^d	Post-op Wk 36 optional ^d	Post-op Wk 48 ^d	Off Study ^b
Axillary Lymphadenectomy alone, Axillary Lymphadenectomy with STR OR Axillary Lymphadenectomy + LYMPHA^a		X						
Informed consent	X							
Demographics	X							
Medical history	X							
Physical exam	X		X	X	X	X	X	
Vital signs ^f	X	X	X	X	X	X	X	
Height	X		X	X	X	X	X	
Weight	X		X	X	X	X	X	
LYMQOL Patient questionnaire	X					X	X	
Limb volume	X						X	X
Skin Thickness Measurements	X					X	X	
Bioimpedance Spectroscopy (LDex)	X					X	X	
ICG Lymphography		X				X	X	
Adverse event evaluation		X						X

a: Investigation: LYMPHA procedure
b: Off-study evaluation.
c: +/- 1 week
d: +/- 4 weeks
e: demographics refers to first name, last name, MRN, DOB
f: vital signs include BP and HR, with RR and temperature as optional vital signs

A Randomized Clinical Trial of the LYMPHA procedure for the Prevention of Lymphedema after Axillary Lymphadenectomy

10. MEASUREMENTS

10.1 Primary outcome measure: Incidence of lymphedema

The primary endpoint in this study is a binary outcome variable defined as the presence of lymphedema at Month 12 (“Yes”/”No”), based on the fulfilment of at least one of the following three criteria: (1) More than 10% increase in the relative excess volume of the affected limb; (2) More than 50% time delay of ICG migration from the injection points to the axilla of the affected upper limb in comparison with the contralateral healthy upper limb; or (3) Aggravation of one or more stages in Yamamoto’s classification of the dermal back flow and morphology of the lymphatic collectors.

The efficacy of the LYMPHA procedure will be determined by comparison between the LYMPHA group (Group C) and lymphadenectomy group (Group A).

10.2 Secondary Outcomes: Other metrics of lymphedema

10.2.1 The comparison of lymphedema rates in the three groups by pairwise comparison.

10.2.2 The ratio of ipsilateral:contralateral skin thickness measured by large skinfold calipers

10.2.3 The ratio of R0 in the ipsilateral:contralateral limbs measured using BIS

10.2.4 The excess volume pairwise comparison between the LYMPHA group and each of the two control groups. We will also compare the excess volume between the two control groups.

10.3 Secondary Outcome: Quality of life

10.3.1 LYMQOL Total score

10.3.2 Measurement time points will be at postoperative clinic visits, which will occur at 1 week and every 3 months for a duration of 12 months.

10.3.3 Response is not the primary outcome

11. REGULATORY CONSIDERATIONS

11.1 Institutional Review of Protocol

The protocol, the proposed informed consent and all forms of participant information related to the study (e.g, advertisements used to recruit participants) will be reviewed and approved by the Stanford IRB and Stanford Cancer Institute Scientific Review Committee (SRC). Any changes made to the protocol will be submitted as a modification and will be approved by the IRB prior to implementation. The Protocol Director will disseminate the protocol amendment information to all participating investigators.

A Randomized Clinical Trial of the LYMPHA procedure for the Prevention of Lymphedema after Axillary Lymphadenectomy

11.2 Data and Safety Monitoring Plan

The Stanford Cancer Institute Data and Safety Monitoring Committee (DSMC) will be the monitoring entity for this study. The DSMC will audit study-related activities to determine whether the study has been conducted in accordance with the protocol, local standard operating procedures, FDA regulations, and Good Clinical Practice (GCP). This may include review of the following types of documents participating in the study: regulatory binders, case report forms, eligibility checklists, and source documents. In addition, the DSMC will regularly review serious adverse events and protocol deviations associated with the research to ensure the protection of human subjects. Results of the DSMC audit will be communicated to the IRB and the appropriate regulatory authorities at the time of continuing review, or in an expedited fashion, as needed.

11.3 Data Management Plan

The Protocol Director and her research team, will prepare and maintain adequate and accurate participant case histories with observations and data pertinent to the study. Study specific Case Report Forms (CRFs) will document treatment outcomes for data analysis. Case report forms will be developed using the REDCap system. The REDCap system is encrypted and compliant for PHI per Stanford University Regulations.

12. STATISTICAL CONSIDERATIONS

12.1 Statistical Design

The objectives of the study are to assess the efficacy of the LYMPHA procedure when compared to the results of wound closure alone and wound closure with soft tissue reinforcement in similar clinical cohorts. We plan to enroll a total of 100 patients in this randomized parallel clinical trial.

The hypothesis to be tested is that adjunctive surgical use of LYMPHA with an axillary lymphadenectomy will produce a superior effect in terms of lymphedema prevention when compared to the effect of an axillary lymphadenectomy alone and an axillary Axillary lymphadenectomy with STR. The primary endpoint, incidence of lymphedema at month 12, will be compared between LYMPHA and the control, axillary lymphadenectomy alone arm using a significance level of 5%.

12.1.1 Randomization

Since this study was started with two groups (A and C), and randomized 13 patients to the control group A and 14 patients to the treatment group C. However, 7 of the 14 patients that were randomized to treatment group C did not receive LYMPHA surgery, were considered screen fails, Therefore in the preliminary assessment, 27 patients will be used in intent-to-treat (ITT) analysis, however, 7 screen fails will not be counted in the per protocol (PP) analysis. In the new 3-arm phase, the randomization procedures will happen during ALND surgery time. and 90 subjects will be allocated in a 1:1:1 randomization into three groups. The clinic staff obtaining measurements will be blinded to the treatment group.

A Randomized Clinical Trial of the LYMPHA procedure for the Prevention of Lymphedema after Axillary Lymphadenectomy

12.2 Preliminary assessment

Since the study has stopped 2-arm recruitment and will start the new 3-arm recruitment, the current collected 2-arm data will be used to conduct a preliminary assessment, to check the comparability, safety and efficacy of the trial.

Preliminary assessment will evaluate the primary endpoint (presence of lymphedema) and secondary endpoints (skin thickness, BIS, and LYMPQOL). Both intent-to-treat (ITT) analysis and per protocol (PP) analysis will be explored.

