12.4.2 Analysis Plan

Fisher's exact tests will be used to determine significance of differences in lymphedema rates between LYMPHA and the lymphadenectomy alone control arm, and significance of differences in lymphedema rates between LYMPHA and the lymphadenectomy with STR control arm. If treatment arms differ significantly at baseline in demographics (for e.g. age), lymphedema status at the end of treatment will be compared between treatment groups via a logistic regression, using the necessary covariates. Depending on the attrition rate, we may also use mixed effects logistic regression models to determine whether the treatment arms significantly differ in the binary endpoint (lymphedema status). Mixed models automatically handle missing data, producing unbiased estimates as long as observations are missing at random. This allows the use of all available data from all subjects, thereby minimizing the effects of loss to follow-up.

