12.6.2 Sample size justification

The risk of lymphedema development is considered to be 30% in the surgical control group (group A), and studies have shown it is to be reduced to 4% when LYMPHA is applied during an axillary lymphadenectomy [12, 30]. With N=40 subjects (20 subjects per arm A and C) in the first stage, the power to stop after the first stage is 56%. Finally, with additional N=40 subjects (20 subjects per arm A and C) in the second stage, the overall power to stop at either the first or the second stage is 88%.

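### The preliminary efficacy look (12.2), the stop option (12.6.2) and the undivided 5% level (12.1) are not joined up, so control of the 5% level is not shown

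*Protocol*

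**What the plan says.** - **12.2, Preliminary assessment.** After the two-arm recruitment closed, "the current collected 2-arm data will be used to conduct a preliminary assessment, to check the comparability, safety and efficacy of the trial". The assessment takes in the primary endpoint as well as the secondary ones, and "Both intent-to-treat (ITT) analysis and per protocol (PP) analysis will be explored". No test, threshold, stop or claim is attached to it.
- **12.1.1 and 3.4.** The patients at that point are 13 in Group A and 14 in Group C. Seven of the 14 did not receive LYMPHA and drop out of the per-protocol set, leaving 13 v 7. A further 90 patients are then randomized 1:1:1, which is 30 per arm.
- **12.1, Statistical Design.** The primary endpoint "will be compared between LYMPHA and the control, axillary lymphadenectomy alone arm using a significance level of 5" per cent. The text does not say whether this is one- or two-sided, or whether it is the overall level or the level of the last test only.
- **12.4.2.** "Fisher's exact tests will be used to determine significance of differences in lymphedema rates between LYMPHA and the lymphadenectomy alone control arm".
- **12.4.1.** The ITT set takes in all participants, so the 27 may be counted again at the end.
- **12.6.2.** With 20 per arm in a first stage, "the power to stop after the first stage is 56" per cent. With 20 more per arm, the power to stop at one stage or the other is given as 88%. No boundary is stated.

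**The concern.** The sample-size section describes a trial that can stop at a first look. The only interim efficacy look in the protocol is the preliminary assessment. The significance level in 12.1 makes no mention of a look. Read together, these sections leave it possible to call LYMPHA effective on the first 27 patients, or to call it effective at the end with the full 5%, and nothing rules out doing both.

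This goes beyond detail that a statistical analysis plan would normally supply, because the protocol's own parts do not fit together. The power figures presuppose a divided 5%, and neither the section that sets the level nor the section that plans the look carries that division. The look also falls at 13 v 14, not at the 20 v 20 on which the power to stop was computed, and it is taken in two analysis sets without naming the one that governs.

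At stake is the false-positive rate for the primary comparison.

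**Working it through.** **Inputs.** Risks of 30% (Group A) and 4% (Group C), and stages of 20 then 40 per arm cumulative, from 12.6.2. Look sizes 13 v 14 and 13 v 7, and a new phase of 30 per arm, from 12.1.1. Fisher's exact test from 12.4.2. Level 5% from 12.1. Assumptions: two-sided tests; the final C v A comparison is either 43 v 44 (27 patients pooled: 13 + 30 v 14 + 30) or 30 v 30 (new patients only).

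**Step 1: reproduce the protocol's power.** Unpooled variance: 0.30 × 0.70 + 0.04 × 0.96 = 0.2484. The expected z is 0.26 / √(0.2484/20) = 2.333 at stage 1 and 0.26 / √(0.2484/40) = 3.299 at stage 2. The correlation between looks is √(20/40) = 0.707. With a Pocock critical value of 2.178 at both looks (nominal two-sided 0.0294 each, 5% overall):

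- stage 1: 1 − Φ(2.178 − 2.333) = 56.2%
- either stage: 1 − Pr(Z1 < 2.178 and Z2 < 2.178) = 88.2%

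Other choices tried:

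| Boundary | Stage 1 | Either stage |
|---|---|---|
| Stated in 12.6.2 | 56% | 88% |
| Pocock, 2.178 at both looks | 56.2% | 88.2% |
| Pocock-type spending function, 2.157 / 2.201 | 57.0% | 87.8% |
| 1.96 at both looks, unpooled variance | 64.5% | 92.0% |
| 1.96 at both looks, pooled variance | 59.0% | 88.6% |
| O'Brien-Fleming | 32.1% | 90.8% |
| Fisher at 0.05 at both looks | 50.0% | 87.8% |

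Of these, only the Pocock-type boundaries come close on both figures. The sizing therefore assumed a split of the 5%.

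**Step 2: type I error at the sizes that apply.** With a common risk p in both arms, sum over all outcomes (x of 13, y of 14) the binomial probability b(x; 13, p) × b(y; 14, p), times 1 if the look has Fisher p ≤ 0.05, and otherwise times the probability that the final Fisher test has p ≤ 0.05 given (x, y). For the per-protocol look, split the 14 into 7 + 7 independent patients and also count a rejection at 13 v 7. Maximum over common risks of 0.20 to 0.50:

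| Success can be claimed at | 43 v 44 at the end | 30 v 30 at the end |
|---|---|---|
| ITT look (0.05) or final test (0.05) | 6.4% | 5.8% |
| ITT look, per-protocol look or final test | 7.3% | 6.7% |

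At the protocol's 30% risk with pooling, the two rows are 6.3% and 7.2%. With no claim at the look, the final test alone is at most 3.9% (43 v 44) and lower for 30 v 30.

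**Step 3: milder readings.** A look at 0.0294 followed by a final test at the full 0.05 gives 4.7% at a 30% risk and at most about 5.1% over other risks (43 v 44). Two unadjusted Fisher looks at the planned 20 then 40 per arm give at most 4.6%. A look at 0.001 followed by 0.05 gives at most 3.9%.

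**Step 4: what the look can show.** Take Group A at 30%, the seven treated Group C patients at 4% and the seven untreated at 30%. Fisher's test at 0.05 then has 9.0% power in the ITT set and 4.7% in the per-protocol set. The chance that the ITT lymphedema rate in Group C is no better than in Group A is 17%.

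**The case against.** A reader might infer that the 5% level is broken. The documents do not support that.

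- Section 12.2 ties no test, stop or claim to the look, and calls the ITT and per-protocol analyses exploratory in effect. Sections 2.4 and 12.2 start the three-arm phase whatever the look shows. A look without consequence leaves the error of the final test unchanged.
- No section calls the preliminary assessment the first stage of 12.6.2, and the sizes differ. The two-stage text may simply be left over from the two-arm design.
- Since 56% and 88% fit a boundary that holds 5% overall, the stop option was evidently sized with error control. The 5% in 12.1 can be read as the overall level.
- Fisher's test is conservative. If the look were taken at 0.0294 and the final test at the full 5%, the error would be about 5%. The figures of 5.8% and above need an unadjusted claim at the look, which no section states.

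All of this stands, and it rules out a statement of breach. It does not close the gap, because each reassuring reading has to be supplied by the reader.

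A reader might also infer that results by arm will reach the unblinded surgeons and colour their intraoperative eligibility judgement. Section 2.4 says that surgeons know the allocation. It does not say that they receive interim results, and it places randomization after that judgement. Disclosure is therefore undocumented and is not part of this point, though a sentence on access would be prudent.

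**Conclusion.** The point holds in a limited form: control of the 5% level is not shown, because three sections that should describe one testing scheme do not. The excess is conditional. It is 0.8 to 1.4 percentage points above 5% (5.8% to 6.4%) if success may be claimed at 0.05 at the ITT look or at the end, and 1.7 to 2.3 points (6.7% to 7.3%) if the per-protocol look may count too. It is nil if the look carries no consequence.

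These figures assume two-sided Fisher tests, equal true risks of 20% to 50%, per-protocol exclusions unrelated to outcome, and the LYMPHA v lymphadenectomy-alone comparison only. Whether the 27 patients enter the final set is also an assumption, so both cases are given. With about 9% power in the ITT set and 5% in the per-protocol set, a tested look offers little in return for the uncertainty it creates.

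**What to change.** Preferred, before the look is run:

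- **12.2:** state that primary-endpoint results from the 27 patients are tabulated without a test and support no success claim, stop or design change. Keep arm-level efficacy results with the DSMC and the statistician until the last Month 12 visit.
- **12.1:** state that the 5% is spent once, at the final analysis.
- **12.6.2:** remove the two-stage stopping text and restate the power for the single final test in the set that will be used.

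If a tested look is kept instead, state its boundary, the analysis set that governs and the level of the final test. As an example, 0.001 at the look with 0.05 at the end keeps the overall Fisher error at or below 3.9%.

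The cost is wording in three sections and the loss of an early efficacy p-value. The restated power may also fall below 88%. With 30 v 30 and a pooled-variance z-test (mean risk 0.17), (0.26 × √30 − 1.96 × √(2 × 0.17 × 0.83)) / √0.2484 = 0.77, which is about 78% power.

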12.2 Summary of analyses

Preop visit: After obtaining written consent, medical history, current medications, and allergies will be reviewed, height/weight/VS, physical exam by PI will be conducted, limb measurements performed (volume, BIS, skin thickness), ICG lymphography, and LYMPQOL survey completed.

T1 (1 week following surgery): physical exam, VS, height, weight, photos, symptoms/AE review.

T2 (6 months following surgery): physical exam, VS, height, weight, photos, symptoms/AE review.

T3 (Optional 9 months following surgery): physical exam, measurements (volume, BIS, skin thickness), ICG lymphography, LYMPQOL survey, VS, height, weight, photos, symptoms/AE review.

T4 (12 months following surgery): physical exam, measurements (volume, BIS, skin thickness), ICG lymphography, LYMPQOL survey, VS, height, weight, photos, symptoms/AE review.

Primary endpoint (rate of lymphedema based on volume analysis and ICG analysis) and secondary endpoints (BIS, skin thickness, ICG lymphography and LYMPQOL survey) will be evaluated at final analysis.

12.3 Descriptive Statistics and Exploratory Data Analysis

Preliminary analyses will include graphical methods to check for outliers to identify errors and highly unusual values and to check assumptions needed for analysis, such as normality. Normally distributed variables will be summarized by mean and standard deviation and compared between the three treatment arms using ANOVAs. Non-normally distributed variables will be summarized by median and interquartile range and compared using the Kruskal Wallis test.

A Randomized Clinical Trial of the LYMPHA procedure for the Prevention of Lymphedema after Axillary Lymphadenectomy

12.4 Primary Analysis

The efficacy of the LYMPHA procedure will be determined by the comparison of the lymphedema rates in the LYMPHA group and the lymphadenectomy alone control group, and by the comparison of the lymphedema rates in the LYMPHA group and the lymphadenectomy with STR control group

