2.4 Study Design

We propose a randomized clinical trial to determine the efficacy of the LYMPHA procedure in breast cancer patients undergoing axillary lymphadenectomy.

Up to 100 subjects will be enrolled in the trial; they will undergo either lymphadenectomy, lymphadenectomy with soft tissue reinforcement (STR) or lymphadenectomy with LYMPHA. Subjects must meet all additional defined inclusion and exclusion criteria.

Please note that soft tissue reinforcement is common practice and used as the standard of care in some lymphedema centers. The addition of this group is important because it allows a comparison of LYMPHA to a currently commonly practiced alternative and the ability to assess for superiority of the LYMPHA procedure. In short, at Stanford, we perform soft tissue reinforcement with collagen scaffolding commonly and would like to start including these patients in our prospective analysis/study.

All patients that are enrolled will be randomized into one of three groups: Group A (surgical control group 1) – the patients will undergo lymphadenectomy alone with simple wound closure, Group B (surgical control group 2) – the patients will undergo lymphadenectomy with soft tissue reinforcement using a collagen scaffold, or Group C (treatment group) - the patients will undergo lymphadenectomy and LYMPHA at the time of wound closure as an adjunct to lymphadenectomy procedure.

Randomization will occur after it has been determined that patients are eligible for the trial intraoperatively. Patients are deemed eligible for the trial intraoperatively if ALND is performed and there are available lymphatics to bypass.

The study will be double blind and randomized. Each patient will be randomized to either the treatment or control group 1 or 2 and will be blinded to their group. While the surgeons will not be blinded, all personnel who track outcomes in clinic will be blinded. The primary outcomes that the protocol is designed to evaluate include efficacy, safety, and impact on the quality of life.

The study was started with 2-arm design (Group A and Group C). A preliminary assessment to the trial effects will be conducted using the current collected data. After the revised protocol is approved, the study will recruit subjects in the new 3-arm phase: 90 subjects (30 subjects per arm in the three groups (Groups A, B, C)

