12.5 Secondary Analysis

Secondary endpoints include skin thickness, BIS and quality of life as measured by the LYMQOL. We will also compare the lymphedema rates in the three groups by pairwise comparison as a secondary analysis.

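### The primary comparison is fixed in two ways: sections 10.1 and the 12.1 test use LYMPHA versus lymphadenectomy alone, while 12.4, 12.4.2 and the 12.1 hypothesis add LYMPHA versus soft tissue reinforcement

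*Protocol*

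**What the plan says.** The protocol describes the comparison that decides efficacy in several places, and they do not agree.

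- **C versus A only.** Section 10.1: "The efficacy of the LYMPHA procedure will be determined by comparison between the LYMPHA group (Group C) and lymphadenectomy group (Group A"). In section 12.1 the test sentence names only the comparison of LYMPHA with the "axillary lymphadenectomy alone arm using a significance level of 5"%. Section 12.6.2 gives power for arms A and C only.
- **C versus A and C versus B.** Section 12.4 determines efficacy by C versus A "and by the comparison of the lymphedema rates in the LYMPHA group and the lymphadenectomy with STR control group". Section 12.4.2 gives each comparison its own Fisher's exact test, the second for the "significance of differences in lymphedema rates between LYMPHA and the lymphadenectomy with STR control arm". The hypothesis in 12.1 is superiority "when compared to the effect of an axillary lymphadenectomy alone and an axillary Axillary lymphadenectomy with STR". Section 2.4 justifies adding Group B because "it allows a comparison of LYMPHA to a currently commonly practiced alternative and the ability to assess for superiority of the LYMPHA procedure".
- **The same comparisons again as secondary.** Section 10.2.1 lists "The comparison of lymphedema rates in the three groups by pairwise comparison", and 12.5 says "We will also compare the lymphedema rates in the three groups by pairwise comparison as a secondary analysis".

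Section 12.7 sets criteria for success but does not settle the matter. It speaks of a single control group and lists limb volume, skin thickness, bioimpedance, lymphatic pattern and quality of life, not the binary lymphedema endpoint.

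**The concern.** Sections 10.1 and 12.4 both say what determines efficacy, and they give different sets of comparisons. No section ranks them. Section 12.4 also leaves open whether both comparisons must succeed, one is enough, or two results are simply reported side by side.

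The verdict on the trial can turn on this:

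- If C beats A but not B, efficacy is shown under 10.1. It is not shown under 12.4 read as 'both', which is the reading the 12.1 hypothesis favours.
- If C beats B but not A, efficacy is not shown under 10.1. It is shown under 12.4 read as 'either'.
- If 12.4 only means two separate reports, the verdicts do not clash, but the protocol does not say so.

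An analysis plan could not resolve this by adding detail. Whichever rule it adopted would contradict one section of the protocol.

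**Working it through.** **Inputs.** Lymphedema risk is 30% in A and 4% in C (12.6.2). The three-arm phase has 30 per arm (2.4). Fisher's exact test comes from 12.4.2 and the 5% level from 12.1. Two assumptions are needed. The test is taken as two-sided, because 12.1 gives no sidedness. The Group B rate is taken as 10% to 30%, because the protocol gives none.

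**The protocol's own power.** Take a two-look Pocock boundary (two-sided 5%, critical z = 2.178 at each look) with unpooled variance. The boundary is inferred; the protocol does not name one.

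- Stage 1, 20 per arm: z = 0.26 / √[(0.30×0.70 + 0.04×0.96)/20] = 2.333. Power = Φ(2.333 − 2.178) = 56.2%; stated 56%.
- Stage 2, 40 per arm: z = 0.26 / √[0.2484/40] = 3.299. With correlation √½ between looks, overall power is 88.2%; stated 88%.

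The stated figures thus reproduce as a two-arm C versus A design and do not cover C versus B.

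**C versus A at 30 per arm.** For c events in C, let a(c) be the smallest number of control events giving p ≤ 0.05 in favour of C. For example, 0 versus 6 gives p = 2×C(30,6)/C(60,6) = 0.024, and 0 versus 5 gives 0.052, so a(0) = 6.

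Power = Σ P(C = c) × P(A ≥ a(c)).

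| c | a(c) | P(C = c) | P(A ≥ a(c)) | Product |
|---|---|---|---|---|
| 0 | 6 | 0.2939 | 0.9234 | 0.2714 |
| 1 | 8 | 0.3673 | 0.7186 | 0.2639 |
| 2 | 9 | 0.2219 | 0.5685 | 0.1262 |
| 3 | 11 | 0.0863 | 0.2696 | 0.0233 |
| 4 | 12 | 0.0243 | 0.1593 | 0.0039 |

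With the small remainder for c ≥ 5, the sum is 68.9%.

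**The readings of 12.4.** Group C is shared, so

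P(both) = Σ P(C = c) × P(A ≥ a(c)) × P(B ≥ a(c)).

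| Assumed B rate | Both succeed | C beats A only | C beats B only |
|---|---|---|---|
| 30% | 51.9% | 17.0% | 17.0% |
| 20% | 23.5% | 45.4% | 5.2% |
| 10% | 2.2% | 66.7% | 0.3% |

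The third column is how often 10.1 and 12.4 disagree if 12.4 means 'both'. The fourth is how often they disagree if it means 'either'.

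**If the two-arm patients are pooled.** Section 12.4.1 puts all participants in the ITT analysis, which may bring in the 27 two-arm patients (13 A, 14 C), although 12.1.1 and 12.2 use them for the preliminary assessment. That gives 43 A, 44 C and 30 B. Assume 30% risk in the 7 Group C patients who did not receive LYMPHA and 4% in the other 37. C versus A then has 73.7% power.

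| Assumed B rate | Both succeed | C beats A only | C beats B only |
|---|---|---|---|
| 30% | 51.0% | 22.7% | 11.3% |
| 20% | 21.6% | 52.1% | 2.5% |
| 10% | 2.7% | 71.0% | 0.1% |

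**Type I error under 'either'.** With a common risk of 10% to 50% in all arms, a false claim in favour of C occurs in 0.9% to 2.5% of trials at 30 per arm and 3.0% to 3.7% pooled.

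**The case against.** The strongest reply is that the text leans one way. C versus A is the only comparison in 10.1, the only one given the 5% level and the only one powered, while C versus B also appears among the secondary comparisons. A reader could take C versus A as confirmatory and C versus B as additional. That is a sensible reading, and the fix follows it. But it does not override a section headed Primary Analysis or the hypothesis in 12.1. Sections 10.2.1 and 12.5 cover all three pairs, C versus A included, so they cannot demote C versus B alone.

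Other points stand in part:

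- Neither 10.1 nor 12.4 words a pass/fail rule. What conflicts is the set of comparisons that determines efficacy; 'both' and 'either' are readings.
- 'Either' has thin support, since 12.4 and the 12.1 hypothesis join the comparisons with 'and'. It also carries no serious error inflation.
- The 45% and 67% depend on an assumed Group B rate and largely reflect that C versus B has little power (about 29% at B 20% and 2.5% at B 10%).
- The pooled case rests on further assumptions, and 4.2 provides for removing and replacing patients who do not receive the intervention. If every Group C patient had 4% risk, C versus A power would be about 89% to 90% at 43 or 44 per arm.
- Testing order and multiplicity detail can be left to an analysis plan. The contradiction over which comparisons are primary cannot.

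**Conclusion.** The concern holds. The protocol gives two incompatible sets of primary comparisons and no rule for choosing between them. The harm is a success criterion that can be picked once results are known; false-positive inflation is not the issue.

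The size depends on the reading and on the unknown Group B rate. Under 'both', the verdict differs from that under 10.1 in about one trial in six (B 30%) to two in three (B 10%) at 30 per arm. Under 'either', it differs in 17% down to 0.3%. Under separate reporting there is no clash. These figures assume two-sided Fisher tests at 5% and the protocol's 30% and 4%. The contradiction itself rests on the text alone.

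**What to change.** In 12.4 and 12.4.2, make C versus A the single primary comparison at the 5% level, in line with 10.1, the 12.1 test sentence and the arms powered in 12.6.2. Make C versus B a key secondary comparison, tested at 5% only if C versus A is significant. Align 10.2.1, 12.1 (including its hypothesis) and 12.5.

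If superiority over STR is meant to be part of the primary claim, state instead in 10.1, 12.1, 12.4 and 12.4.2 that both comparisons must succeed, and give the power for that with an assumed Group B rate.

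This is a text amendment and needs no new data. Under the first option, superiority over STR becomes a secondary claim, although 2.4 gives it as a reason for adding Group B. A significant C versus B result is lost whenever C versus A fails: 17%, 5% or 0.3% of trials at 30 per arm for B at 30%, 20% or 10% (pooled: 11%, 2.5% or 0.1%). The amendment does not make the 88% in 12.6.2 apply to 30 per arm, because that figure describes two stages of 20 per arm; at 30 per arm C versus A has 69%.
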